15. EFFICACY OUTCOMES

Per protocol, patients may have multiple target lesions treated. For patient level endpoints, only one lesion per patient is required to meet the criteria for the endpoint. All endpoints are summarized on a patient level, except when noted.

For the binary primary and selected secondary endpoint event rates to be calculated, the denominator will include only patients who have either had the event by the time of interest (end of the visit window), or had follow-up (starting from the beginning of the visit window) for the endpoint. Visit windows are defined in Section 7.5.

For example, at the 1 year analysis (day 365), only patients who have either had the event by day 365 + 14 = 379 or had follow-up up to day 365 - 30 = 335 will be included in the analysis for the endpoint. In this example, if a patient has an event at day 10 post procedure, the patient will be included in the 1 year analysis and counted as an event. However, if a patient drops out of the study at day 10 post procedure without an event (e.g., due to withdrawal of consent) the patient will not be included in the analysis.

All events as reported by the CEC as well as by the sites will be listed.

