15.2.1. SECONDARY EFFICACY VARIABLES & DERIVATIONS

15.2.1.1. Device, Lesion, and Procedure Success at Time of Baseline Procedure

 Device success is defined as achievement of a final in-stent residual diameter stenosis of <50% by Quantitative Coronary Angiography (QCA) in the target lesion, using the assigned device only and without a device malfunction. Device malfunctions are defined as occurring during the time of use.
 From final procedure QCA, Residual Diameter Stenosis (DS):

DS = 100*(1-mean (MIN1, MIN2) / mean (IS1, IS2)

Where 1 refers to projection = Projection 1

2 refers to projection = Projection 2

MIN: In stent minimum lumen diameter

IS: interpolated reference vessel diameter

If DS <50% and no device malfunction then Device Success = 1

Else if DS>=50% then Device Success = 0.

 Lesion success is defined as achievement of a final in-stent residual diameter stenosis of <50% (by QCA) in the target lesion using any percutaneous method.

From final procedure QCA, Residual Diameter Stenosis (DS) is calculated using the formula given above and:

If DS <50% then Lesion Success = 1

Else if DS \geq 50% then Lesion Success = 0.

Procedure success is defined as achievement of a final in-stent diameter stenosis of <50% (by QCA) using the assigned device and/or with any adjunctive devices, without the occurrence of cardiac death, Q wave or non-Q wave MI, or repeat revascularization of the target lesion during the hospital stay. Each Event is defined from adjudication, with peri-procedural MIs adjudicated per SCAI [2] definition.

The analysis of device success and lesion success will be performed on lesion level, i.e., the numerator will be the number of target lesions meeting the criteria for device or lesion success, respectively, and the denominator will be the total number of target lesions.

The analysis of procedure success will be performed on patient level, i.e., the numerator will be the number of patients with all target lesions meeting the criteria for procedure success and the denominator will be the total number of patients.

These analyses will be performed by Cardiovascular Research Foundation.

Document: T:\PROJ\Medinol\CXA27472\06 Biostatistics\Documentation\SAP\Final

1.0_08Aug2018\JNIR01_SAP_Final V1.0_08Aug2018.docx

Author: [name] Version Number: Final V1.0 Version Date: 08Aug2018

Template No: CS TP BS016 Revision 4 Reference: CS WI BS005

Effective Date: 01Apr2016

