Category	Definite	Definite stent thrombosis is confirmed by either angiographic* or pathologic† analysis
	Probable	Probable stent thrombosis is considered to have occurred after intracoronary stenting for either: • any unexplained death within the first 30 days unless that patient had baseline procedure for ST elevation MI • any MI, irrespective of time after baseline procedure, that is related to documented acute ischemia in the territory of the implanted stent without angiographic confirmation of stent thrombosis and in the absence of any
		other obvious cause
	Possible	Possible stent thrombosis is considered to have occurred with any unexplained death from 30 days after intracoronary stenting until end of trial follow-up
** 5 6 4	, ,	
i * ⊺: Refer to	protocol Sec	ction 21.1

15.2.2. **ANALYSIS OF SECONDARY EFFICACY VARIABLES**

Selected secondary efficacy data will be analyzed as binary variables and summarized with patient counts (or lesion counts as appropriate), percentages, and exact 95% confidence intervals. Treatment group differences will be summarized with 95% confidence intervals. These binary variable summaries will be provided for:

- Device, lesion, and procedure success rates
- Stent thrombosis by category, timing and type
- Site reported bleeding events

The clinical secondary endpoints will be analyzed as time to event variables.

The secondary endpoints will not be formally tested for non-inferiority and testing will be considered descriptive.

Refer to Sections 15.2.2.1 and 15.2.2.2 for details

15.2.2.1. **Analysis of Binary Variables**

For the summary of secondary endpoints as binary variables by time point, only patient who had the event by the time of interest (end of the visit window for that time point), or had follow-up (starting from the beginning of the visit window) for the endpoint will be included in the analysis. Visit windows are defined in Section 7.5.

Binary secondary endpoints will be compared between treatment groups using a Chi-square test (twosided) and Wald 95% CI will be provided for the difference. Fisher's exact p-value (two-sided) and corresponding CI for difference will be provided when at least one cell has an expected frequency of less than five.

The difference in proportion (95% CI) will be reported.

Document: T:\PROJ\Medinol\CXA27472\06 Biostatistics\Documentation\SAP\Final

1.0_08Aug2018\JNIR01_SAP_Final V1.0_08Aug2018.docx

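### Device and lesion success are analysed per lesion with methods that ignore clustering within patients, so their intervals are somewhat too narrow if lesions in the same patient are positively correlated

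*SAP*

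**What the plan says.** SAP 15 notes: "Per protocol, patients may have multiple target lesions treated". Protocol 6.4.6 caps this at two target vessels with two lesions each, so four per patient. SAP 15.2.1.1 states: "The analysis of device success and lesion success will be performed on lesion level", and "the denominator will be the total number of target lesions". Procedure success alone is counted per patient, with every target lesion required to succeed.

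SAP 15.2.2 says selected secondary data are "summarized with patient counts (or lesion counts as appropriate), percentages, and exact 95% confidence intervals" and lists "Device, lesion, and procedure success rates" among them. SAP 15.2.2.1 adds: "Binary secondary endpoints will be compared between treatment groups using a Chi-square test", and "Wald 95% CI will be provided for the difference". Fisher's exact p-value with a matching interval takes over when an expected cell count is below five.

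Neither document specifies a clustered variance, GEE, mixed model or cluster bootstrap, and neither gives a patient-level version of device or lesion success. SAP 7.5 and 15.2.2 class all secondary testing as descriptive.

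**The concern.** Protocol 6.4.4 plans for all target lesions to be treated in the baseline procedure. Two lesions in one patient therefore usually share anatomy, operator and session, and positive correlation of their outcomes is the natural expectation. The exact, chi-square, Wald and Fisher methods all take each lesion as an independent observation. With positive correlation, the lesion count overstates the information in the data.

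At stake is the stated precision of two named secondary endpoints and of their comparison with BIONICS. The lesion-level percentages themselves are not affected.

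**Working it through.** The plan states no precision or power for device or lesion success, so there is no figure of its own to reproduce.

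**Inputs from the documents**
- About 100 JNIR patients (SAP 4.1), matched 4:1 to BIONICS (SAP 15.1.2), so 100 against 400 patients.
- At most four target lesions per patient (Protocol 6.4.6).
- Lesions per patient in earlier bare-metal-stent studies: 280/278 = 1.01 (Protocol 3.3.1) and 354/318 = 1.11 (Protocol 3.3.3).
- Device success in those studies: 98.2% and 98.9%. Lesion success was 280/280 in the first.

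**Assumed, because not given:** lesions per patient in JNIR, the within-patient correlation (ICC), and a success rate of 95% as a less favourable case.

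**Design effect.** With k lesions per patient, deff = 1 + (E[k²]/E[k] − 1) × ICC. If a share q of patients have two lesions and the rest one, the mean is 1 + q and the bracket equals 2q/(1 + q). Interval width scales roughly with √deff.

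| Mean lesions | 2q/(1+q) | ICC | deff | √deff |
|---|---|---|---|---|
| 1.01 (280/278) | 0.014 | 0.5 | 1.007 | 1.00 |
| 1.11 (354/318) | 0.203 | 0.5 | 1.10 | 1.05 |
| 1.2 | 0.333 | 0.3 | 1.10 | 1.05 |
| 1.3 | 0.462 | 0.5 | 1.23 | 1.11 |
| 1.5 | 0.667 | 0.8 | 1.53 | 1.24 |

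Recomputing the exact interval at the reduced sample size gives a widening of up to about 6% in the second row.

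**Example.** Take 100 patients, 120 lesions and 114 successes (95%). The unadjusted exact interval is 89.4% to 98.1%. The adjusted intervals use an effective sample size of 120/deff:
- ICC 0.3, n = 120/1.10 = 109: 89.1% to 98.3% (width × 1.05).
- ICC 0.5, n = 120/1.17 = 103: 88.8% to 98.3% (× 1.09).
- ICC 1, n = 120/1.33 = 90: 88.3% to 98.5% (× 1.17).

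**Coverage by simulation** (40,000 runs, 100 against 400 patients). The scenarios are the last three rows of the table: 1.2 lesions with ICC 0.3, 1.3 with 0.5, and 1.5 with 0.8.
- Single-group exact interval, 95% success: about 96%, between 95% and 96%, and about 91%. At 98% success it is about 97% or more in all three.
- Wald interval for the difference, 95% success: about 92%, 90.5% and 87%, against about 93% with ICC 0.
- Chi-square type I error, 95% success: about 6%, 7.5% and 11%, against about 5% with ICC 0. These figures apply chi-square in every run and ignore the switch to Fisher's test.
- Less favourable case, two lesions in every patient and 98% success: exact-interval coverage is 93.2% at ICC 0.3 and 90.3% at ICC 0.5.

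**Which test applies.** With 120 JNIR lesions and 2% failures, the expected JNIR failures are 120 × 0.02 = 2.4, below five. At 98% success and 1.1 to 1.3 lesions per patient, Fisher's test replaces chi-square in about 99% or more of runs. At 95% success and 1.2 lesions it does so in about a fifth of runs.

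**The case against.** The strongest reply is that little changes in practice. The only lesion counts in the documents are close to one per patient, where the widening is small. Earlier success rates were about 98% or higher, and there the exact interval is conservative enough to absorb moderate clustering. At those rates Fisher's test, also conservative, would usually replace chi-square. Procedure success already gives a patient-level rate close to lesion success. Nothing is decided on these intervals.

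Most of this stands, and it limits the point. It does not remove it. The earlier studies treated with bare-metal stents, whereas JNIR admits complex and restenotic lesions and up to four targets, so 1.01 to 1.11 is a low anchor and not a ceiling. Fisher's test also assumes independent lesions. Procedure success adds in-hospital events and does not exclude device malfunction, so it replaces neither endpoint.

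Three stronger readings are tempting but not supported:
- **A nominal 95% interval covers only 94% down to 89%.** That follows from the normal approximation 2Φ(1.96/√deff) − 1 for the three assumed scenarios. It does not describe the exact interval that the SAP specifies, which is conservative near 100%.
- **The intervals are 24% too narrow.** That is the far corner of an assumed range; the documents give neither the lesion count nor the ICC.
- **All the shortfall of the Wald interval is clustering.** At 95% success it covers only about 93% even with ICC 0.

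**Conclusion.** The point holds in a limited form. The plan ignores clustering for device and lesion success, and the direction of the error is clear if some patients have several lesions and outcomes within a patient are positively correlated. Its size is unknown from the documents: about 0 to 6% at the earlier studies' lesion counts with ICC up to 0.5, and 5 to 24% under the assumed 1.2 to 1.5 lesions and ICC 0.3 to 0.8. Any real loss of coverage falls mainly on the Wald interval and the chi-square test when success is near 95%.

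This is a minor reporting matter. A reader might infer that the main result is affected. It is not: SAP 15 counts TLF per patient, and only TLF at 12 months is formally tested.

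**What to change.** Amend SAP 15.2.1.1 and 15.2.2 as follows.
1. Keep the lesion-level percentages.
2. Add patient-level device and lesion success, defined as all target lesions successful, with an exact 95% interval and the planned group comparison. This follows the rule already used for procedure success. It also fits Protocol 7.2.2, which speaks of patient counts only; the move to lesion counts is not among the changes listed in SAP 4.3.
3. Take lesion-level intervals and comparisons from a patient-clustered method that works near 100%: an exact interval at the effective sample size (lesions divided by the design effect), or a cluster-robust variance when there are enough failures. State in advance how the design effect is obtained, since an ICC cannot be estimated well from a handful of failures. Setting ICC to 1 gives an upper limit that depends only on the lesion counts.
4. When failures are few or none, rely on the patient-level exact interval. A percentile bootstrap then has zero or unreliable width (lesion success of 280/280 would give an interval of no width at all), and GEE may not converge.

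The cost is a few sentences, minor programming and slightly wider intervals. No new data are needed.

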15.2.1.2. Clinical secondary endpoints defined from CEC adjudication data

The following secondary clinical endpoints as adjudicated by the CEC will be evaluated at 30 days, 6 months, and 1, 2, 3, 4, and 5 years, except as noted:

- TLF at 30 days, 6 months, and 2, 3, 4 and 5 years defined as the composite of cardiac death, target vessel related MI, or clinically-driven TLR.
- Major adverse cardiac events (MACE; the composite rate of cardiac death, any MI or clinically-driven TLR)
- Target vessel failure (TVF; the composite rate of all-cause death, target vessel related MI or clinicallydriven TVR)
- All-cause mortality
- Cardiac death
- Myocardial infarction
- · Target vessel related MI
- Clinically-driven TLR: TLR is defined as any repeat percutaneous intervention of the target lesion or bypass surgery of the target vessel (i.e. revascularization) performed for clinically driven restenosis or other complication of the target lesion.
- Clinically-driven TVR: TVR is defined as any repeat percutaneous intervention or surgical bypass of any segment of the target vessel (i.e. revascularization) performed for clinical driven restenosis.
- Stent thrombosis: Stent thrombosis is defined according to timing, type, and degree of certainty per ARC definition (Table A:). Stent thrombosis should be reported as a cumulative value at the different time points and with the different separate time points. Time 0 is defined as the time point after the guiding catheter has been removed and the patient left the catheterization lab after the baseline procedure. Stent thrombosis will also be reported by ARC category and, in particular, for ARC categories definite and probable.

Table A: ARC Definition of Stent Thrombosis

Timing	Acute	≤ 24 hours post stent implantation
	Subacute	> 24 hours to 30 days post stent implantation
	Late	> 30 days to 1 year post stent implantation
	Very late	> 1 year post stent implantation
Туре	Primary	Occurs in target lesion or margins after baseline procedure
	Secondary	Occurs after revascularization (TLR, TVR, or non-TVR)

Document: T:\PROJ\Medinol\CXA27472\06 Biostatistics\Documentation\SAP\Final

1.0_08Aug2018\JNIR01_SAP_Final V1.0_08Aug2018.docx

Author: [name] Version Number: Final V1.0 Version Date: 08Aug2018

Template No: CS TP BS016 Revision 4 Reference: CS WI BS005

Effective Date: 01Apr2016

Copyright © 2000, 2010, 2012, 2016 Quip

Category	Definite	Definite stent thrombosis is confirmed by either angiographic* or pathologic† analysis
	Probable	Probable stent thrombosis is considered to have occurred after intracoronary stenting for either: • any unexplained death within the first 30 days unless that patient had baseline procedure for ST elevation MI • any MI, irrespective of time after baseline procedure, that is related to documented acute ischemia in the territory of the implanted stent without angiographic confirmation of stent thrombosis and in the absence of any
		other obvious cause
	Possible	Possible stent thrombosis is considered to have occurred with any unexplained death from 30 days after intracoronary stenting until end of trial follow-up
** 5 6 4	, ,	
i * ⊺: Refer to	protocol Sec	ction 21.1

15.2.2. **ANALYSIS OF SECONDARY EFFICACY VARIABLES**

Selected secondary efficacy data will be analyzed as binary variables and summarized with patient counts (or lesion counts as appropriate), percentages, and exact 95% confidence intervals. Treatment group differences will be summarized with 95% confidence intervals. These binary variable summaries will be provided for:

- Device, lesion, and procedure success rates
- Stent thrombosis by category, timing and type
- Site reported bleeding events

The clinical secondary endpoints will be analyzed as time to event variables.

The secondary endpoints will not be formally tested for non-inferiority and testing will be considered descriptive.

Refer to Sections 15.2.2.1 and 15.2.2.2 for details

15.2.2.1. **Analysis of Binary Variables**

For the summary of secondary endpoints as binary variables by time point, only patient who had the event by the time of interest (end of the visit window for that time point), or had follow-up (starting from the beginning of the visit window) for the endpoint will be included in the analysis. Visit windows are defined in Section 7.5.

Binary secondary endpoints will be compared between treatment groups using a Chi-square test (twosided) and Wald 95% CI will be provided for the difference. Fisher's exact p-value (two-sided) and corresponding CI for difference will be provided when at least one cell has an expected frequency of less than five.

The difference in proportion (95% CI) will be reported.

Document: T:\PROJ\Medinol\CXA27472\06 Biostatistics\Documentation\SAP\Final

1.0_08Aug2018\JNIR01_SAP_Final V1.0_08Aug2018.docx

Author: Version Number: Final V1.0 [name] Version Date: 08Aug2018

Template No: CS TP BS016 Revision 4 Reference: CS WI BS005

Effective Date: 01Apr2016

Copyright © 2009, 2010, 2012, 2016 Quintiles Transnational Corp. All rights reserved. The contents of this document are confidential and proprietary to Quintiles Transnational Corp. Unauthorized use, disclosure or reproduction is strictly prohibited.

15.2.2.2. Analysis of Time to Event Variables

Survival analysis techniques will be used to analyze the time-to-event variables. Time to event analysis will be performed for each time point separately (i.e. up to 30 days, 6 months, and 1, 2, 3, 4, and 5 years). Patients without events will be censored at the patients' early withdrawal date or the last known event-free time point. If this event-free time point occurs after the analysis time point, the days to event variable will be set equal to the analysis time point so that the patient will be included in the analysis (e.g. if the last data point for a patient without an event is at 3 years and 1 week, for the 3 year time to event analysis, this patient will be censored at 3 years). When analyzing composite endpoints, time is measured from enrollment to the first event (days).

Kaplan Meier estimated event rate and number of events will be reported at 30 days, 6 months, and 1, 2, 3, 4, 5 years. The following statistics will be reported at the indicated time: log rank p-value, and hazard ratio (Wald's 95% CI) obtained via Cox proportional hazards regression.

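### SAP 15.2.2.2 has no rule for deaths from other causes, so by default they are censored and the Kaplan-Meier rates of most secondary endpoints slightly overstate the share of patients affected

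*SAP*

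**What the plan says.** SAP section 15.2.2 states: "The clinical secondary endpoints will be analyzed as time to event variables". Section 15.2.1.2 lists these endpoints as TLF, MACE, TVF, all-cause mortality, cardiac death, MI, target vessel MI, TLR, TVR and stent thrombosis, to be "evaluated at 30 days, 6 months, and 1, 2, 3, 4, and 5 years, except as noted".

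Section 15.2.2.2 gives one censoring rule: "Patients without events will be censored at the patients' early withdrawal date or the last known event-free time point". For the output, "Kaplan Meier estimated event rate and number of events will be reported" at each of these time points, with a log-rank p-value and a Cox hazard ratio. Neither document says what happens to a patient who dies of a cause outside the endpoint, and neither names a cumulative-incidence or competing-risk method.

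The endpoints differ in which deaths they count. TLF and MACE count cardiac death only. MI, TLR and TVR count no death as such. TVF counts all-cause death.

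Stent thrombosis appears twice. It is a clinical secondary endpoint, and section 15.2.2 also places "Stent thrombosis by category, timing and type" among the binary summaries. For those, section 15.2.2.1 includes "only patient who had the event by the time of interest (end of the visit window for that time point), or had follow-up" from the start of the window. A patient who dies earlier without the event meets neither condition and leaves the denominator.

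**The concern.** Censoring treats a patient as still able to have the event later. That is reasonable for someone who withdraws alive, but not for someone who has died. If deaths from other causes are censored, one minus Kaplan-Meier estimates the risk in a setting where those deaths do not occur. It cannot be lower than the proportion of patients who actually have the event, and it is higher once such deaths happen before other patients' events.

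The gap widens with follow-up, and these rates run to 5 years. They will be read as the share of patients with TLF, MI or repeat revascularization, and placed beside matched BIONICS rates. What is at stake is the accuracy of descriptive long-term rates.

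**Working it through.** The plan states no Kaplan-Meier or cumulative-incidence figure for these endpoints, so there is nothing of its own to reproduce. The check asks how large the gap could be.

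**Inputs from the documents.** 12-month TLF 5.8% (Protocol 7.5). Stent thrombosis 1 to 3% at one year (Protocol 6.1.2). About 100 JNIR patients (SAP 4.1).

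**Assumptions (not in the documents).** TLF after year 1: 1 to 3% per year. MACE: 7% in year 1, then 2.5% per year. Cardiac death: 1% per year. MI, TLR or TVR: 3% in year 1, then 1% per year. Stent thrombosis after year 1: 0.3% per year. Competing death: 0.5 to 4% per year where only non-cardiac death competes, and 1 to 5% per year where any non-event death competes.

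**Formulas.** Each annual risk r becomes a hazard h = −ln(1 − r). With event hazard h1 in year 1 and h2 in years 2 to 5, and competing-death hazard d:

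- 1 − KM at 5 years = 1 − exp(−(h1 + 4·h2))
- Cumulative incidence = h1/(h1+d) · (1 − exp(−(h1+d))) + exp(−(h1+d)) · h2/(h2+d) · (1 − exp(−4(h2+d)))

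**Worked case.** TLF 5.8% in year 1, 2% per year later, non-cardiac death 2% per year.

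- 1 − KM = 1 − 0.942 × 0.98⁴ = 13.11%
- Cumulative incidence = 0.0598/0.0800 × 0.0768 + 0.9232 × 0.5 × 0.1492 = 12.63%
- Overstatement = 0.48 points

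**Results at 5 years (lowest to highest competing death)**

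| Endpoint | 1 − KM | Cumulative incidence | Gap, points |
|---|---|---|---|
| TLF, 1%/yr later | 9.51% | 9.44–8.97% | 0.07–0.54 |
| TLF, 2%/yr later | 13.11% | 12.99–12.17% | 0.12–0.94 |
| TLF, 3%/yr later | 16.61% | 16.43–15.27% | 0.17–1.33 |
| MACE | 15.96% | 15.81–14.81% | 0.15–1.15 |
| Cardiac death | 4.90% | 4.84–4.44% | 0.06–0.46 |
| MI, TLR or TVR | 6.82% | 6.69–6.21% | 0.13–0.61 |
| Stent thrombosis, 1% in year 1 | 2.18% | 2.14–1.99% | 0.04–0.19 |
| Stent thrombosis, 3% in year 1 | 4.16% | 4.11–3.92% | 0.05–0.24 |

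At 1 year the TLF gap is 0.01 to 0.12 points.

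**Binary stent-thrombosis rule.** The rate is taken as events / (events + event-free survivors), evaluated at 5 years. It gives 2.25–2.56% against a true 2.14–1.99%, and 4.31–5.02% against 4.11–3.92%. The overstatement is 0.11 to 0.57 and 0.20 to 1.10 points, larger than under Kaplan-Meier for the same inputs.

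**Against sampling error.** SE = √(p(1−p)/100). For 5-year TLF this is 2.9 points at 9.51%, 3.4 at 13.11% and 3.7 at 16.61%. For MI, TLR or TVR at 6.82% it is 2.5. For stent thrombosis at 2.18% it is 1.5. Each exceeds the gap in its row.

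**The case against.** Most of the case for leaving the plan alone is fair.

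- **The SAP does not say it censors these deaths.** A reader might infer a deliberate rule. The text is only silent. Still, a patient who dies of another cause is a patient without the event, and no other rule applies, so an analyst following the text would censor.
- **Large competing mortality is unsupported for TLF, MACE and cardiac death.** Protocol 21.1 classes a death as cardiac unless a non-cardiac cause is unequivocal. The exclusions also remove patients with life expectancy under 24 months, LVEF below 30% or creatinine clearance below 30 mL/min. The 1.33-point figure needs 4% non-cardiac death per year, or 1 − 0.96⁵ = 18.5% over 5 years, which is unlikely here. The cardiac default gives no relief for MI, TLR and TVR, where cardiac deaths compete too.
- **Not every early death competes with stent thrombosis.** An unexplained death within 30 days counts as probable stent thrombosis unless the baseline procedure was for STEMI.
- **A reader might infer that the comparison with BIONICS is distorted.** With constant hazards and an 8% Kaplan-Meier rate, 5-year competing mortality of 15% in one trial and 5% in the other gives overstatements of 0.61 and 0.20, a net 0.41 points. Nothing in the documents supports such a difference in mortality. The standard error of the difference, √(0.08 × 0.92 × (1/100 + 1/400)), is about 3.0 points.
- **It is partly a choice of target.** The SAP promises a Kaplan-Meier rate, not a share of patients. But Protocol 7.2.2 planned patient counts and percentages, so the share affected is the natural reading.
- **The information is partly visible.** Event counts are printed beside the rates, and all-cause and cardiac mortality are both reported.

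**Conclusion.** A minor point that holds. Following the SAP as written, the Kaplan-Meier rates for TLF, MACE, cardiac death, MI, target vessel MI, TLR and TVR overstate the proportion affected once deaths from other causes occur. So do the stent-thrombosis rates where that endpoint is analysed as time to event. With no such deaths the bias is zero.

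The size rests on assumed mortality and late event rates: about 0.1 point or less at 1 year and roughly 0.04 to 1.3 points at 5 years, with the upper end unlikely for TLF, MACE and cardiac death. No formal decision depends on it. The secondary endpoints are descriptive. The primary 12-month TLF test is a binary comparison that does not use these curves. The log-rank test and Cox hazard ratio remain valid as cause-specific comparisons. The documents do not support reading this as a threat to the trial's conclusion. For stent thrombosis the binary denominator adds a separate upward bias, and correcting the time-to-event section alone would leave that in place.

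**What to change.** In SAP 15.2.2.2:

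- State that death not counted in the endpoint is a competing event: non-cardiac death for TLF, MACE and cardiac death; any non-event death for MI, target vessel MI, TLR, TVR and stent thrombosis. Withdrawal remains a censoring event.
- Report Aalen-Johansen cumulative incidence at each time point for every endpoint except all-cause mortality and TVF, with the Kaplan-Meier rate beside it.
- Keep the log-rank test and Cox hazard ratio, labelled as cause-specific comparisons.

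In SAP 15.2.2.1, for the stent-thrombosis summaries, keep patients who die event-free before the window in the denominator as non-events.

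The cost is a few sentences and one procedure option. For JNIR no new data are needed: the clinical events committee already adjudicates every death and its cardiac or non-cardiac cause (Protocol 14.10 and 14.10.1). The one drawback, weaker comparability with published Kaplan-Meier stent results, disappears when both rates are shown.
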